### **4. Inclusion and Exclusion Criteria**

#### 4.1. Recruitment of Subjects and Inclusion

Subjects who qualify for inclusion will be those potential subjects identified by [name] being seen at the UNM Pain Clinic who are experiencing pain with "suboptimal" pain relief (defined as discussed below in this section) by standard pain treatment. A randomization table for all subjects receiving pramipexole vs. placebo will be generated such that the Clinical Research Coordinator will use as a template when dispensing drug at the time of consent. All types of chronic pain will be considered, and thus, specific types of chronic pain will not be part of the inclusion or exclusion criteria. Non-English, Spanish speaking subjects will be included. Adults 18 yrs. or older will be included. Women who are not post-menopausal or have not undergone an oophorectomy/hysterectomy will be excluded.

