## *Non-opioid pramipexole suppresses immune NLRP3 reactivity for pain*

Initial screening will occur at the time when [name] is evaluating the patient in the pain clinic. The Electronic Medical Record database is up-to-date and will be viewed at the time of the clinical evaluation. Data that will be evaluated and collected are: sex, weight, height, age, race/ethnicity, years post-menopausal, prior oophorectomy/hysterectomy, years under pain treatment, pain diagnosis (etiology), and type of insurance.

At the time [name] is evaluating a patient that meets the inclusion criteria, 3 standardized questions will be asked:

- (1) Are you happy with the amount of pain relief so far?
- (2) Would you like to try something else to improve your pain relief?
- (3) Are you able to do everything you want to do with the current treatment?

At this time, systemized exclusion criteria will be evaluated as noted in the table below.

Based on the Electronic Medical Record, [name] will have access to information regarding prior history of renal impairment. If [name] suspects the possible presence of renal impairment, a blood panel will be evaluated prior to potential patient participation.

As indicated in the Inclusion/Exclusion Criteria table, Patients with Parkinson's Disease or patients who are taking prescription medications that act as dopamine agonists are excluded from the study.

Note that only those patients who are pregnant will be excluded. A pregnancy test at the time of enrollment and at mid-term (end of 2 weeks of the 4 week study) when subjects check in with the Clinical Research Coordinator. The second pregnancy test will act to mitigate risks of false negative pregnancy test results at the time of enrollment..

4.2. children, a particular racial or ethnic group, etc. and provide justification.

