27.5.5. If the research involves pregnant women

N/A

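### Section 4.1's eligibility statements, read naturally, conflict for a non-pregnant, pre-menopausal woman with no oophorectomy or hysterectomy

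*Combined protocol and SAP*

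**What the plan says.** Section 4.1 deals with women's reproductive status in two places.

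- The opening paragraph, after admitting adults aged 18 or over, says: "Women who are not post-menopausal or have not undergone an oophorectomy/hysterectomy will be excluded".
- Later in Section 4.1, just before Section 4.2, the text says: "Note that only those patients who are pregnant will be excluded". It provides for a pregnancy test at enrolment and another at the mid-term visit, with this reason for the second: "The second pregnancy test will act to mitigate risks of false negative pregnancy test results at the time of enrollment".

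Other text in Section 4.1 bears on how the two fit together.

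- The data reviewed at the initial screen include "years post-menopausal, prior oophorectomy/hysterectomy, years under pain treatment".
- When the clinic physician "is evaluating a patient that meets the inclusion criteria, 3 standardized questions will be asked", and at that time "systemized exclusion criteria will be evaluated as noted in the table below". That table does not appear in the text available for this review.
- Patients with Parkinson's disease are excluded, and "patients who are taking prescription medications that act as dopamine agonists are excluded from the study".

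Section 27.5.5, headed "If the research involves pregnant women", is answered as not applicable.

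**The concern.** A coordinator or clinician applying Section 4.1 to a pre-menopausal woman who is not pregnant and has had neither operation meets two sentences that point in opposite directions. Enrolling her follows the later one and breaks the earlier one. Refusing her does the reverse.

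The question should arise in practice. Section 4.2 aims for equal numbers of men and women, and Section 5.6 says there is no screening after recruitment, so whichever rule is applied at the clinic visit decides the matter. The rule also determines whether women who could become pregnant may receive pramipexole. If the opening paragraph governs, none of these women is enrolled. If the later sentence governs, they may be, with the two tests as the visible safeguard. A known pregnancy is a bar under either sentence.

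**Working it through.** The plan gives no figure to reproduce; the check is a comparison of text.

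**Step 1: the scope of "only".** The later sentence cannot mean that pregnancy is the trial's sole exclusion, because the same part of Section 4.1 also excludes Parkinson's disease and dopamine-agonist use. It introduces the pregnancy tests, so its natural scope is exclusion on child-bearing grounds. The rest of the check uses that scope.

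**Step 2: the scope of "or".** The opening sentence has two readings. The ordinary one excludes a woman who is neither post-menopausal nor surgically treated. The literal one excludes a woman who lacks either attribute, and so would also bar a post-menopausal woman who has had no surgery.

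**Step 3: apply each rule to a non-pregnant woman.** Two yes/no attributes give 2 × 2 = 4 combinations.

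| Post-menopausal | Prior surgery | Opening sentence, ordinary | Opening sentence, literal | Later sentence |
|---|---|---|---|---|
| yes | yes | in | in | in |
| yes | no | in | out | in |
| no | yes | in | out | in |
| no | no | **out** | **out** | **in** |

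The opening sentence disagrees with the later one in 1 of 4 combinations on the ordinary reading and in 3 of 4 on the literal reading. Only the last row disagrees under both, and the point is confined to it. The later sentence admits that woman by implication; it does not name her.

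**Step 4: look for text that settles it.**

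- Collecting menopausal and surgical history at the screen fits the opening sentence, since those are the data needed to apply it.
- The stated reason for the second test supposes that an enrolled woman might be pregnant. That leans towards the later sentence, but a test can also be a precaution among women who satisfy the opening one.
- The not-applicable answer in Section 27.5.5 fits both rules.
- No other visible section says which rule governs.

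**Step 5: size.** The documents give no age or menopausal distribution for the clinic population, so the number of affected women within the target of 30 completers (up to 45 recruited) cannot be derived, and no count is offered.

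**The case against.** The best answer is that the two sentences work in sequence. The first sits under a heading about recruitment and inclusion, and the exclusion check is described for a patient who already meets the inclusion criteria. Among women who have passed the menopausal and surgical restriction, only those found pregnant are then removed on child-bearing grounds. Read this way both sentences hold. Applying every listed exclusion cumulatively, which is the usual practice, leads to the same place: the woman in question stays out and no fetus is exposed.

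Two further arguments support this. The later sentence follows shortly after references to the Inclusion/Exclusion table and may be a gloss on one of its rows, so its scope cannot be judged fully without that table. The tests are also compatible with the restriction: the opening paragraph sets no minimum time since menopause, and the history comes from the record and the clinic evaluation, so testing women who pass it is a reasonable safeguard.

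Much of this stands. The sequential reading is available, the tests are weak evidence for admitting these women, and the table could fix the scope of the later sentence. But the reading is not compelled. The opening sentence itself speaks of exclusion, no visible text sets out a two-step order for women, and a reader who takes the later sentence at face value would admit someone the earlier one bars.

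A reader might go further and infer that the sentences cannot be reconciled whatever the table says. The documents do not support that, given the sequential reading and the unseen table.

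**Conclusion.** The point holds in limited form. On their natural reading, the two statements in Section 4.1 give opposite answers for one group: non-pregnant, pre-menopausal women without oophorectomy or hysterectomy. A reconciling reading exists but is not stated. Confidence is medium, because the table that might settle the scope is not visible. This is an ambiguity in an eligibility rule with a safety bearing. It should be corrected, but it falls short of a critical defect. No sample size, power, alpha or analysis figure is affected.

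The conclusion rests on two assumptions: that "only" in the later sentence concerns child-bearing grounds, and that the unseen table and consent pages have not already made one rule explicit.

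Two stronger inferences should be resisted. One is that the trial will expose women of child-bearing potential to the drug; that follows only if the later sentence governs, and the screening data collected point the other way. The other is that the plan lacks a contraception requirement or an action on a positive test; either may stand in the table or the consent form, so their absence from the visible text shows nothing.

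**What to change.** **Preferred change.** Keep the safer restriction in the opening paragraph of Section 4.1 and reword it so that its "or" cannot mislead: *Women who are neither post-menopausal nor have undergone oophorectomy/hysterectomy will be excluded.* Delete the later sentence that limits exclusion to pregnancy. Keep both pregnancy tests, described as a precaution.

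**Alternative, if the sponsor means to admit women of child-bearing potential.** Delete the restriction in the opening paragraph and reword the later sentence to say simply that pregnant patients will be excluded. Keep both tests. Add a rule to stop study drug on a positive test, and a contraception requirement, in each case only if the table or consent form lacks it.

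Under either choice, confirm that the Inclusion/Exclusion table and the consent form carry the same rule.

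**Cost.** The preferred change rewords one sentence and deletes one. The alternative deletes one and rewords one, with up to two conditional additions. Each needs a check of the table and consent wording. Neither alters the planned sample size or the analysis.

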## *Non-opioid pramipexole suppresses immune NLRP3 reactivity for pain*

Initial screening will occur at the time when [name] is evaluating the patient in the pain clinic. The Electronic Medical Record database is up-to-date and will be viewed at the time of the clinical evaluation. Data that will be evaluated and collected are: sex, weight, height, age, race/ethnicity, years post-menopausal, prior oophorectomy/hysterectomy, years under pain treatment, pain diagnosis (etiology), and type of insurance.

At the time [name] is evaluating a patient that meets the inclusion criteria, 3 standardized questions will be asked:

- (1) Are you happy with the amount of pain relief so far?
- (2) Would you like to try something else to improve your pain relief?
- (3) Are you able to do everything you want to do with the current treatment?

At this time, systemized exclusion criteria will be evaluated as noted in the table below.

Based on the Electronic Medical Record, [name] will have access to information regarding prior history of renal impairment. If [name] suspects the possible presence of renal impairment, a blood panel will be evaluated prior to potential patient participation.

As indicated in the Inclusion/Exclusion Criteria table, Patients with Parkinson's Disease or patients who are taking prescription medications that act as dopamine agonists are excluded from the study.

Note that only those patients who are pregnant will be excluded. A pregnancy test at the time of enrollment and at mid-term (end of 2 weeks of the 4 week study) when subjects check in with the Clinical Research Coordinator. The second pregnancy test will act to mitigate risks of false negative pregnancy test results at the time of enrollment..

4.2. children, a particular racial or ethnic group, etc. and provide justification.

We will attempt to enroll an equal number of males and females. There are no race- or ethnic specific questions in this protocol. However, in an attempt to include a balanced approach for enrolling non-Caucasian and Caucasian populations participating in this clinical trial, approximately 50% of the study subjects will make up these two populations. An attempt to enroll African American and Native American (American Indian) populations that will make up the remaining 50% of the study population will be planned to reflect the unique cultural and ethnic diversity of Albuquerque. A review of this targeted enrollment progress in this area will be made quarterly, and if minority recruitment is not meeting expectations by the end of the 2nd quarter, further guidance from the CTSC will be utilized.

Diverse socioeconomic backgrounds will also be an important factor for inclusion. The UNM Clinical Neuroscience Center serves a diverse population, and recruitment will occur among all represented groups.

#### **INCLUSION OF CHILDREN**

This research study will include only individuals 18 years of age and older because chronic pain is rare in pediatric populations. The mechanism underlying its development is not typically expressed until adulthood. Any pediatric chronic pain cases encountered are thus likely to have a substantial idiopathic component. This factor along with the small sample would make results interpretation difficult or impossible for pediatric patients.

“Suboptimal pain relief/ scores” is vague because the Brief Pain Inventory address two discrete aspects of pain: (1) pain severity and (2) pain interference that are subjectively evaluated (Tan, Jensen et al. 2004, Walton, Beattie et al. 2016). The scores obtained from aspects of the scale (items 1-6) that evaluate pain severity and the quality of the pain (burning vs. aching) focuses on current or recent pain. However, the scores obtained from aspects that target affective and physical interference (item 9 with 7 subscales) of pain experience and provides a more complete evaluation of issues surrounding quality of life that are frequently (but not always) considered more critical to patient’s pain experience. Item #8 of the pain scale (“In the past 24 hours, how much pain relief have pain treatments or medications provided? Please circle the percentage that most shows how much relief you have received”) targets the key issue of “suboptimal” pain relief, but only in the past 24 hrs, and provides a “snapshot” of the patient’s chronic pain relief. Therefore, while it may seem to oversimplify the patient’s level of pain relief, patient scores 5 or greater on most items in the Brief Pain Inventory will be considered “suboptimal”.

### **5. Number of Subjects**

- 5.4. All subjects will be recruited from the UNMH outpatient population from the UNMH Pain Center.
- 5.5. The target sample size is 30 subjects with complete data. The investigators may recruit up to 45 patients to allow for any dropouts.
- 5.6. All subject recruited will participate. There will be no screening after recruitment.

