## **9. Resources Available**

- 9.4. The PI and study staff have received training for clinical trials. [name] (PhD) is a basic scientist conducting the cell assays and interpreting the data results. [name](PhD) is a basic scientist directing the CTSC core for conducting the cell assays and interpreting the resultant data. [name] (PhD) is a statistician and familiar with clinical trials designs, and [name] (MD) is a physician who specialized in pain treatment at the UNMH Pain Clinic.
- 9.5. [name], MD will be responsible for medical decision-making and ordering and evaluation of necessary diagnostics and therapeutics.
- 9.6. [name] treats 15-30 patients daily at the UNMH Pain Clinic. With this high access to patients, the goal of enrolling 30 patients during an 11 month period is predicted to be very feasible.

All 30 recruited patients will be needed with no further screening.

An estimated 6 hrs per patient will be devoted to consent, completing surveys, blood draw, scheduling and dispensing the pramipexole or placebo by the Clinical Research Coordinator.

- The facilities used will be at the CTSC where consent, enrollment, scheduling visits, obtaining blood samples, completion of the Brief Pain Inventory survey, dispensing drugs at initiation and at midterm (end of week 2,) and collecting unused drug at termination. For the biological assays from human cell lines or from blood samples, the clinical laboratory arm of the CTSC, Center for Molecular Drug Discovery, will be used.
- The availability of medical and/or psychological resources that subjects might need as a result of an anticipated consequences of the human research will be available by [name] or by referral from [name]. The anticipated consequences of the research will be (1) improved pain relief, (2) no change in pain relief, or (3) a worsening of pain. [name] will continue to monitor patients after the study is terminated, as these patients will continue to receive outpatient care from the pain clinic.

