Patient recruitment, assessment of Brief Pain Inventory (BPI): Pain scores and blood draws will be conducted at the CTSC Participant Clinical Interactions Unit with the CTSC Clinical Research Coordinator. Blood samples collected by the CTSC Clinical Research Coordinator will be analyzed at the Center for Molecular Discovery by personnel from [name] lab, trained by personnel from the Center for Molecular Drug Discovery (Director; [name], co-I). Personnel from the [name] lab have expertise in inflammatory marker analysis from PBMCs [57, 58]. All freshly collected blood samples will be frozen and stored by the Clinical Research Coordinator at the CTSC Clinical Laboratory and will be transported to the Center for Molecular Drug Discovery once ALL of the samples for the study (all 30 patients) have been collected. This is to allow for assay to be conducted at the same time to avoid potential effect of 'time of assay' that may impact data.

All subjects will therefore meet with the CTSC Clinical Research Coordinator for a total of 3 times; at the initiation of the study, at mid-term when the second batch of drug is dispensed and unused drug is returned, and at termination for a second and final blood draw and providing all completed Brief Pain Inventory surveys (5/patient). At the termination of the study, patients will turn in their paper copies of the Brief Pain Inventory questionnaire completed for each week of the study (total 4 weeks). Original data records are important to demonstrate all necessary physical documentation of the study.

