## **15. Withdrawal of Subjects**

Anticipated circumstances where subjects may be withdrawn from the research without their consent may be if their pain scores worsen for longer than a week.

In the event of early withdrawal, patients will be tapered from 0.5 (if currently taking that dosage) to 0.250 for 1 week. However, according to the manufacturer's (Boehringer Ingelheim, Inc) packet information, pramipexole at doses of up to 0.75 once daily can be discontinued without taper.

While there are no contraindications associated with pramipexole, the collection and reporting of adverse are as follows:

The collection and reporting of adverse events will occur at: (1) the time of the phone conversation at the end of weeks 1 and 3 with the CRC who will collect the Brief Pain Inventory scores, (2) at the end of week 2, the time of the mid-term in-person meeting with the CRC when the subject will provide the scores of the BPI for that week and will pick up drug dispense #2, (3) At the final in-person with the CRC, at the termination of the study at week 4, and (4) at any point during the study when the subject calls the CRC to report an adverse event or when the subject calls [name]. All adverse events will be recorded by the CRC and kept with the subject's study records.

See actions upon evidence of symptomatic orthostatic hypotension above (Section 14, "Provisions to monitor the data to ensure the safety of subjects"), and other adverse

reactions will be monitored during dose escalation during weeks 1-2, as well as throughout the 4-week study. Monitored will occur as detailed in “Collection and Reporting of Adverse Events”.

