## **24. Consent Process**

*Consent will be obtained by the CTSC Clinical Research coordinator at the CTSC. obtaining consent, and if so describe:*

Each subject will be informed at the time of consent:

Subject name and other identifying information will be maintained in locked files, available only to authorized members of the research team, for the duration of the study. For any information entered into a computer, the only identifier will be a unique study identification (ID) number. Any personal identifying information and any record linking that information to study ID numbers will be destroyed 3 years after the study completion. Information resulting from this study will be used for research purposes and may be published; however, the subject will not be identified by name in any publications.

Information from the subject's participation in this study may be reviewed by the investigators only, and by the UNM Human Research Review Committee (HRRC), which provides regulatory and ethical oversight of human research. The subject's name will not be used in any published reports about this study.

A discussion with each subject will include ensuring that the subject can withdraw from this study at any time without affecting your access to healthcare.

The investigators may end subject's participation in this study if determined that it is in the subject's best interest or the study's best interest to stop subject participation.

Each subject will be informed of their right to withdraw from the study and related information. Their authorization for the use and disclosure, within the research team, of health information (subject name, date of birth, address, telephone numbers, race/ethnicity. The Brief Pain Inventory survey) for this study shall not expire unless subject cancels this authorization. Health information will be used or disclosed within the research team as long as it is needed for this study. Subjects will be informed that they may withdraw authorization at any time, but will need to be done in writing.

*Subjects not fluent in English*

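### The only sample definition is 30 subjects with complete data and no Phase II analysis set is named, so the plan leads to a completers' comparison although completion depends partly on the primary outcome

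*Combined protocol and SAP*

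**What the plan says.** Section 5.5 states: "The target sample size is 30 subjects with complete data. The investigators may recruit up to 45 patients to allow for any dropouts". This is the only place where the Phase II sample is defined.

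Two other sections use the figure 30 differently. Section 9.6 treats it as the number recruited: "All 30 recruited patients will be needed with no further screening". Section 12 says that frozen blood samples go to the assay laboratory "once ALL of the samples for the study (all 30 patients) have been collected", so that everything is assayed at one time.

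Section 7.4 makes the BPI the primary endpoint and the blood mRNA and protein measures secondary. Under Section 12 the BPI is completed five times per patient (baseline and weeks 1 to 4), and blood is drawn at baseline and week 4.

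On stopping, Section 15 anticipates that "subjects may be withdrawn from the research without their consent may be if their pain scores worsen for longer than a week". Section 24 lets the investigators end participation "if determined that it is in the subject's best interest or the study's best interest to stop subject participation".

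Section 13 names one statistical method, a three-way repeated-measures ANOVA, and it is for the Phase I cell experiments. Its Phase II part covers groups, follow-up, dosing and capsules. It gives no test, analysis population or handling of missing BPI scores.

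**The concern.** When a protocol names no analysis set, the analyst falls back on whatever definition of the sample it does contain. Here that is complete data. Conventional repeated-measures ANOVA, the only method named anywhere in the protocol, also drops a subject with any missing score in its usual form. Both routes end with completers.

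That would matter less if completion had nothing to do with pain. Under Section 15, a subject whose pain scores worsen for more than a week may be taken out, and pain scores are what the primary endpoint measures. Section 24 adds discretionary stops. If the two arms lose different kinds of patient, the completers are no longer comparable groups, and recruiting further completers does not make them so. Both the BPI and the blood comparisons would be affected.

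Part of the loss could not be undone. Section 17 has unused blood samples destroyed at the study's termination date, so a dropout's sample that is not assayed by then is gone.

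**Working it through.** **What the recruitment figures imply.** The protocol gives no significance level, power, effect size, SD or dropout rate for Phase II, so 30 cannot be derived from stated inputs. The ceiling follows from 30 if the dropout rate d satisfies 30/(1 − d) = 45, so d = 15/45 = 33.3%. For comparison:

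- 10% dropout: 30/0.9 = 33.3, so 34
- 20% dropout: 30/0.8 = 37.5, so 38
- 30% dropout: 30/0.7 = 42.9, so 43

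At the ceiling, up to one third of randomised subjects would fall outside a set of 30 completers.

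**Bias in a simple case.** Assume no drug effect and a normally distributed change score. One arm loses its worst fraction p, and the other loses subjects at random. The random arm's completer mean does not move. The selected arm's completer mean improves by φ(z)/(1 − p) SD, where z cuts off the worst fraction p:

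- p = 0.10: 0.1755/0.90 = 0.195 SD
- p = 0.20: 0.2800/0.80 = 0.350 SD
- p = 1/3: 0.3636/0.667 = 0.545 SD

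The direction depends on which arm loses its worst patients.

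**Less extreme cases.** A simulation with no drug effect used 6,000 runs, 23 v 22 randomised (1:1 assumed, because the ratio is not stated), 15 lost, and a two-sided 5% t-test on completers. Weighted means that worse scores are more likely, but not certain, to be lost. The difference is first arm minus second, in SD units, with higher scores worse.

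| Lost, first v second arm | Mechanism | Mean difference | False-positive rate |
|---|---|---|---|
| 8 v 7 | random in both | 0.00 | 4.6% |
| 10 v 5 | random in both | 0.00 | 4.8% |
| 8 v 7 | weighted in both | −0.04 | 8.6% |
| 10 v 5 | weighted in both | −0.25 | 14.9% |
| 12 v 3 | weighted in both | −0.47 | 29.3% |
| 8 v 7 | weighted in first, random in second | −0.42 | 25.2% |
| 8 v 7 | random in first, weighted in second | 0.38 | 20.9% |

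Random dropout does no harm, even when the counts are unequal. Outcome-related dropout does harm when its extent or its cause differs between arms, and similar counts in the two arms do not rule that out.

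**What a completers' analysis would discard.** A subject who stops after the week 2 visit should already have given three of the five BPI scores (baseline, week 1, week 2).

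**The case against.** The strongest reply is that Section 5.5 is an ordinary recruitment allowance. Recruiting extra subjects to cover dropout is normal and compatible with analysing everyone randomised. On this view the gap is an analysis plan not yet written, which is forgivable in a proof-of-concept trial. Much of that stands, and it limits what can be claimed.

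- A reader might infer that the protocol excludes and replaces dropouts. It says neither, and describes no replacement procedure. The completers' comparison is where the text leads for want of any other rule. It is not a stated choice.
- A reader might take Section 12 to define a completers-only assay set. The sentence sets when samples are shipped, and its 30 may simply be the recruited headcount of Section 9.6, not updated to 45.
- A reader might object to ending enrolment on a count of completers. That does not by itself bias the arm comparison. The harm comes from leaving out those who stopped.
- A reader might treat 0.55 SD as the expected bias, or convert it to BPI points and set it against the 3-point goal in Section 12. The figure is near the worst case: it needs the full allowance used, one arm losing exactly its worst third, and random loss in the other. The 3-point goal is a target for the individual patient's pain control, not a difference between arms.

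The reply does not meet the combination of a sample defined by completion with a withdrawal rule tied to the pain score.

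**Conclusion.** The point holds as a gap that the text fills badly. The only sample definition is completion, nothing else governs the Phase II analysis, and the protocol's own withdrawal rule makes completion depend partly on the primary outcome. The resulting comparison can be biased if dropout differs by arm in extent or reason.

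The size cannot be known in advance. It is near zero if dropout is random in both arms, and about 0.2 to 0.55 SD if one arm loses its worst 10% to 33% while the other loses subjects at random. These figures assume no drug effect and normal change scores. The protocol gives no expected dropout rate or pattern by arm, so they show what is possible and do not forecast it. Separately, the figures of 30 and 45 in Sections 5.5, 9.6 and 12 do not agree.

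**What to change.** 1. In Section 5.5, state that 30 subjects with complete data is a planning expectation, and that the primary analysis includes all randomised subjects (up to 45) in their assigned arm.
2. In the Phase II part of Section 13, name a repeated-measures model that uses every weekly BPI score obtained and keeps subjects with partial data, such as a likelihood-based mixed model. State its missing-data assumption. Report dropout by arm and reason, and give the completers' result as supportive only.
3. In Section 12, provide for assay of the samples from all randomised subjects, before the destruction date in Section 17.
4. Reconcile 30 and 45 in Sections 5.5, 9.6 and 12.

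No rule fixing the number randomised in advance is needed, and no patients are added beyond the 45 already allowed.

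The cost is some analysis work and a few more assays: at the ceiling, 15 further baseline samples plus any week 4 samples obtained from those who stopped. That is modest, but the protocol describes itself as not funded. A baseline sample alone gives no change value, so the gain for the blood endpoints is smaller than for the BPI.

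One limit remains. The result still rests on an assumption about scores after withdrawal. That assumption is more plausible where recorded worsening led to the stop than where the reason lies outside the BPI, so the reasons need to be reported.
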